4 TRIAL DESIGN

Observational study using historic data and stored samples from a multi-centre randomised controlled trial (TARGET, ISRCTN 14024829), where each participant will act as a case (additional tests applied to stored samples) and an internal control (initial outcomes using standard testing only).

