10 STATISTICS AND DATA ANALYSIS

The independent variable is the availability of BAP1, p16 FISH and MTAP testing (binary; available *vs* not available). The primary outcome is identification of malignancy on biopsy (binary; diagnostic *vs* non-diagnostic), with diagnosis defined as i) histopathological confirmation on standard testing or ii) histopathological features of PM with demonstrated BAP1, p16 or MTAP deletion or iii) Multi-disciplinary Team (MDT) diagnosis. It is assumed that confirmation of a malignant diagnosis stops the diagnostic pathway with no additional biopsies required. Any subsequent biopsies for these participants will not be included in the analysis, preventing double-counting. Secondary outcomes include total number of biopsies required, time to diagnosis, stage at diagnosis, number of MDT discussions, biopsy-associated costs, biopsy-related adverse events and survival. Potential confounding variables include age, sex, biopsy method and tumour histology and these will be adjusted for, when possible, in the analysis.

Outcome measures will be tabulated for standard and proposed pathways and compared using descriptive statistics (including the McNemar test). Univariable and multivariable logistic regression will look for an association between the availability of these tests and likelihood of a diagnostic biopsy. The relationship between secondary outcomes and availability of the tests will be evaluated using adjusted and unadjusted regression analyses and time to event analysis (cox proportional hazard model).

Sample Size:

Total number of patients: 59

Total histological samples for analysis: 129 (all participants had multiple biopsies)

REPLICA

IRAS ID 329574

Each participant will be assessed as a case (proposed pathway) and as an internal control (standard pathway) generating two groups of 59 = 118 records for inclusion in the study

Sample size is determined by the number recruited to the TARGET study which demonstrated diagnostic sensitivity (without these additional tests) of 30%. A sample size of 118 (59 in each arm) will allow detection of an increased diagnostic rate of 60% with 95% confidence intervals of +/- 8.8% (based on BAP1 loss prevalence of 60%).

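### The logistic and Cox models take two records per participant with no paired or clustered form named, and adjust for variables that cannot confound a self-controlled comparison

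*Protocol*

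**What the plan says.** Section 4 of the protocol sets a self-controlled design: "each participant will act as a case (additional tests applied to stored samples) and an internal control (initial outcomes using standard testing only"). Section 10 gives "Total number of patients: 59" and describes the pairing as "generating two groups of 59 = 118 records for inclusion in the study". The exposure is the pathway: "The independent variable is the availability of BAP1, p16 FISH and MTAP testing", coded as available or not.

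For the primary binary outcome, Section 10 lists the McNemar test among the descriptive statistics and then states: "Univariable and multivariable logistic regression will look for an association between the availability of these tests and likelihood of a diagnostic biopsy". For the secondary outcomes it names "adjusted and unadjusted regression analyses and time to event analysis (cox proportional hazard model"). On covariates it says: "Potential confounding variables include age, sex, biopsy method and tumour histology and these will be adjusted for, when possible, in the analysis".

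No conditional, mixed, GEE, stratified or cluster-robust form is named for any of these models. Nor does the section say whether McNemar or the logistic model governs the primary conclusion.

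**The concern.** Test availability varies only within a participant, so any regression on it must use both records of the same person. Those records are strongly correlated: a diagnosis on standard testing also satisfies the outcome definition in the proposed pathway, so a participant can move from non-diagnostic to diagnostic but not back. A plain logistic or Cox model treats the 118 records as independent and ignores this.

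The adjustment raises a second problem. A confounder must be associated with the exposure. Age, sex and a participant's tumour histology are the same in both records, so they are perfectly balanced across the two pathways. Biopsy method can differ between the records only because one pathway stops earlier, which makes it a consequence of the pathway.

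At stake are precision in a study whose size is fixed at 59, a possible clash between two planned analyses of the primary outcome, and an adjusted odds ratio whose gap from the unadjusted one readers would take for confounding removed.

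**Working it through.** **Inputs from Section 10.** n = 59 participants and 118 records; standard-pathway rate 30%; proposed-pathway rates 60%, 70% and 80%; stated half-widths 8.8, 8.2 and 7.2 points. From the outcome definition: one-way discordance (b = newly diagnosed, c = 0).

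**1. The plan's own precision figures.** Half-width = 1.96 × sqrt(p(1 − p)/n).

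| p | n = 118 | n = 59 |
|---|---|---|
| 0.60 | 8.84 | 12.50 |
| 0.70 | 8.27 | 11.69 |
| 0.80 | 7.22 | 10.21 |

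The stated figures match n = 118 (8.27 is printed as 8.2). In its precision statement the plan therefore already treats the two records of a participant as independent.

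**2. Difference in proportions, 30% against 60%.**
- Unpaired SE = sqrt(0.3 × 0.7/59 + 0.6 × 0.4/59) = 0.0873; half-width 1.96 × 0.0873 = 17.1 points.
- Paired SE = sqrt((b + c − (b − c)²)/n) with b = 0.30, c = 0: sqrt(0.21/59) = 0.0597; half-width 11.7 points.
- Ratio of SEs: 0.0873/0.0597 = 1.46.

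**3. Log odds ratio, 18 against 35 of 59** (nearest counts to 30% and 60%). OR = (35 × 41)/(24 × 18) = 3.32.
- Unpaired variance = 1/18 + 1/41 + 1/35 + 1/24 = 0.1502; SE 0.388; 95% CI 1.55 to 7.10.
- With nested outcomes the covariance of the two logits is 59/(41 × 35) = 0.0411. Clustered variance = 0.1502 − 2 × 0.0411 = 0.0680; SE 0.261; 95% CI 1.99 to 5.54. A small-sample correction moves this SE only to about 0.263.

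**4. A smaller gain, 18 against 25 of 59** (assumed counts). OR = (25 × 41)/(34 × 18) = 1.67.
- Unpaired variance = 1/18 + 1/41 + 1/25 + 1/34 = 0.1494; SE 0.386; p = 0.18.
- Clustered variance = 0.1494 − 2 × 59/(41 × 25) = 0.0342; SE 0.185; p = 0.005.
- Exact McNemar with 7 discordant pairs, all in one direction: 2 × 0.5⁷ = 0.016.

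**5. Simulation check**, 59 pairs at 30% against 60%, 800 runs. The unpaired SE averages 0.395 against a true SD of about 0.28, and its nominal 95% interval covers more than 99%. The clustered SE averages 0.274 and covers about 95%. The median univariable OR is about 3.55 against a true marginal OR of 3.50.

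**6. Effect of adjusting for a covariate that is the same in both records.** The documents give no covariate strength, so a range is assumed for a normally distributed covariate. Holding the marginal rates at 30% and 60%, the conditional OR is:

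| Assumed log-odds per SD | Conditional OR (marginal 3.50) |
|---|---|
| 0.25 | 3.57 |
| 0.5 | 3.76 |
| 1.0 | 4.52 |
| 1.5 | 5.81 |

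There is no confounding anywhere in this calculation. The whole shift is non-collapsibility.

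**7. Cox model.** The documents give no diagnosis times. With 20 + exponential(60) days and 40% re-diagnosed early, the model SE was 0.186 against a true SD of 0.128. With exponential(90) + 5 days and 30% or 50% of participants shortened to 40% of their time, it was about 0.19 against 0.07 to 0.10. The direction agrees with the logistic result; the size depends on the assumed times.

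**The case against.** **The unpaired reading is inferred.** The protocol never says the records are independent. It speaks of matched data and internal controls, plans McNemar, and a statistical analysis plan could add clustering. This stands in part: the reading is an inference. But Section 10 does more than leave a detail open. It names the models, sets the data out as two arms of 59, and computes its precision on 118, which is the same independence assumption in figures.

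**The error is in the safe direction and a valid test is already planned.** This stands. The naive interval for the pathway effect is too wide and does not manufacture a positive finding, and McNemar would detect the 18 against 25 gain. What remains is lost precision and the absence of a rule for which analysis governs when the two disagree.

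**A reader might infer that every effect estimate is distorted.** The documents do not support that. The univariable odds ratio is a valid marginal odds ratio, and an adjusted one is a legitimate conditional estimate. With a modest covariate the two barely differ. The fault is presenting the adjustment as control of confounding.

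**A reader might also infer that histology exists only for diagnosed participants, so that adjustment conditions on the outcome and drops the rest.** The protocol does not say this, nor that complete-case fitting will be used. Section 7.3 extracts histological and final MDT diagnoses with follow-up to 12 months, and a histology from a later biopsy could be attached to both records. The adjustment is also only promised where possible. Since Section 3 expects some clinico-radiological diagnoses without tissue, histology may be missing for some participants, to an extent the documents do not give.

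**Conclusion.** The point holds in a bounded form. As written, Section 10 places paired records in models with no paired or clustered form, and the pathway-effect standard error comes out too large: by a factor of 1.46 for the difference at 30% against 60%, and 0.388 against 0.261 for the log odds ratio at 18 against 35 of 59. The plan's two analyses of the primary outcome can fall on opposite sides of 0.05.

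None of the four listed covariates can confound test availability. For those constant within a participant, adjustment takes a marginal odds ratio of 3.5 to between about 3.6 and 5.8 over the assumed range of covariate effects.

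The results rest on one-way discordance, which follows from the outcome definition, and on fitting the models as named. The smaller-gain counts, covariate strengths and Cox times are assumptions; for Cox, only the direction is supported. The documents do not support a reading that the plan risks a false positive on the pathway effect or has no valid primary test.

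**What to change.** Amend Section 10 as follows.

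- **Primary analysis:** the paired difference in proportions with a paired 95% interval (Tango or Newcombe), with exact McNemar as the test. State that this governs the conclusion.
- **Time to diagnosis, number of biopsies, MDT discussions and costs:** within-participant differences, with intervals from a bootstrap that resamples participants.
- **Any logistic or Cox model that is kept:** cluster on participant, by GEE or robust variance. Conditional logistic regression is not a remedy, because its odds ratio is infinite when all discordance runs one way.
- **Covariates:** remove the adjustment for confounders. Use age, sex and biopsy method only to describe which participants are re-diagnosed.

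The cost is a wording change to the analysis section. No new data or samples are needed, and the paired analysis is simpler and more precise.

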3 OBJECTIVES AND OUTCOME MEASURES/ENDPOINTS

This research aims to answer the question: Could testing for BAP1, P16 FISH and MTAP IHC have removed the need for further invasive procedures in patients with suspected PM and an initial non-diagnostic biopsy?

We will address this question via the following objectives:

- Identify participants from the TARGET trial population (n=59)
- Extract historic biopsies (initial and repeat) from NHS pathology laboratories (n=129)
- Perform BAP1 and MTAP on all extracted biopsies. Where this fails to yield a diagnosis, perform additional p16 FISH.
- Identify patients for whom additional testing would have yielded a diagnosis, avoiding the need for further invasive tests (primary outcome).
- Investigate whether additional testing would have shortened the overall time to PM diagnosis (secondary outcome).
- Identify TARGET participants who ultimately received a clinico-radiological diagnosis, i.e. no tissue diagnosis was made, in whom additional testing would have provided a definitive diagnosis (sub-group analysis).

Primary and secondary outcomes, and outcome measures can be found in the study summary table.

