6 PARTICIPANT ELIGIBILITY CRITERIA

IRAS ID 329574

All patients recruited for the TARGET study will be included, provided they have sufficient stored biopsy material to undertake the required additional tests.

TARGET eligibility required all of the following to apply:

- Pleural thickening on CT suspicious for pleural malignancy
- Have had any form of pleural biopsy in the last 12 months (either by thoracoscopy or under radiological guidance) which was non-diagnostic for cancer
- Lung Cancer/mesothelioma MDT decision to perform further CT-guided biopsy to pursue a diagnosis

Participants were ineligible for TARGET if ANY of the following applied:

- Unsuitable for a CT guided biopsy (inability to co-operate, lie still for the duration of the biopsy, uncorrectable coagulopathy, inability to tolerate a pneumothorax, severe underlying lung disease [patients with an FEV1 < 35% assessed using simple spirometry])
- Unable to give written informed consent
- Pregnancy or lactation
- Age<18 years
 Pleural thickening not amenable to a radiologically guided biopsy
- Talc pleurodesis in the previous 6 months

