7.3 Data extraction

Baseline clinical information and follow up data from visits at 3, 6 and 12 months will be extracted from the trial database. Where this data is unavailable, it will be sought from medical records. Variables include:

- Baseline demographic data
- Asbestos exposure history
- Relevant medical background
- Biopsy dates and results
- Biopsy method
- Number of biopsies required for diagnosis
- Biopsy-related adverse events
- Histological diagnosis
- Whether diagnosis was tissue based or clinico-pathological.
- Time to diagnosis (from enrolment)
- Stage at diagnosis
- Number of MDT discussions

- MDT outcomes including ultimate MDT diagnosis and date of diagnosis
- Radiological images and reports used during diagnostic period
- Anti-cancer treatment received
- Healthcare utilisation
- Overall survival

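### A Cox hazard ratio does not suit time to diagnosis here: the main gain lies at the index biopsy, where eligibility leaves the standard pathway without events

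*Protocol*

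**What the plan says.** Section 3 makes time a secondary objective: "Investigate whether additional testing would have shortened the overall time to PM diagnosis (secondary outcome". For the secondary outcomes, section 10 names "adjusted and unadjusted regression analyses and time to event analysis (cox proportional hazard model". It gives no event count, target hazard ratio or power for that model.

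Four other statements determine how the model would behave.

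- **Eligibility (section 6).** Every participant had an earlier pleural biopsy "which was non-diagnostic for cancer", and an MDT had decided to pursue a diagnosis with a further biopsy. In the standard pathway nobody is diagnosed at the index biopsy.
- **Where the gain is sought.** The primary objective in the trial summary concerns a definitive diagnosis on the baseline biopsy. Section 10 adds: "It is assumed that confirmation of a malignant diagnosis stops the diagnostic pathway with no additional biopsies required".
- **Time origin (section 7.3).** The variable to be extracted is "Time to diagnosis (from enrolment". Enrolment follows the index biopsy, by up to a year: "Have had any form of pleural biopsy in the last 12 months".
- **Which samples are tested (section 3).** "Perform BAP1 and MTAP on all extracted biopsies". This covers initial and repeat biopsies, 129 in all.

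The same 59 people supply both arms, one record per pathway, and follow-up is 12 months and already complete.

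**The concern.** The two records of one participant differ only if the extra tests bring the diagnosis forward. The largest such shift moves a diagnosis to the index biopsy, a point at which the standard record cannot have one. The treatment effect in the Cox model is therefore concentrated where one arm has no events by design. After that, the two arms share the same people and many of the same dates.

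A hazard ratio assumes a constant relative rate throughout follow-up, and this design rules that out before any data are seen. The time-to-diagnosis objective asks how much sooner people would have been diagnosed. One ratio could mislead on that in either direction, according to where the clock starts. With the origin as written, the tests could appear to give no gain in time, or even a delay, while they save weeks or months.

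**Working it through.** **The plan's own figures.** The only precision figures concern the diagnostic rate. They come from 1.96 × √(p(1−p)/118): 8.84 points at 60% (stated 8.8), 8.27 at 70% (stated 8.2) and 7.22 at 80% (stated 7.2). None bears on the Cox model, so the check below uses assumptions. The Protocol gives no timings.

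**Step 1. Origin at the index biopsy.** The standard pathway has 0 events of 59 there. The proposed pathway has a block of events. The early ratio has no finite value.

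Two sets of assumptions were simulated, with Efron ties and gains at the index biopsy only.

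*Set A* (200 cohorts of 59): 75% malignant; 60% of those diagnosed by the standard route, uniformly over days 44 to 345; index conversions dated day 14; no false positives.

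| Malignant cases converted | HR, cut at 90 days | 180 | 365 | HR after day 30 | Mean days saved to day 365 |
|---|---|---|---|---|---|
| 70% | 12.4 | 4.8 | 2.4 | 0.55 | 130 |
| 50% | 8.5 | 3.3 | 1.9 | 0.75 | 93 |
| 30% | 4.9 | 2.2 | 1.4 | 0.88 | 56 |

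*Set B* (60 cohorts per setting): repeat biopsy 0.5 to 2 months after the index; 30% diagnosed at it; 80% of the rest diagnosed later, after an exponential delay with mean 3 months; index yield unrelated to the standard outcome.

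| Index yield | HR, cut at 0.3 months | 1 | 3 | 6 | 12 |
|---|---|---|---|---|---|
| 20% | none finite | 2.66 | 1.45 | 1.32 | 1.28 |
| 40% | none finite | 5.40 | 2.19 | 1.76 | 1.67 |
| 60% | none finite | 10.0 | 2.89 | 2.58 | 2.35 |

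The early cuts are not planned analyses. They show only that no constant ratio exists.

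**Step 2. Set A by hand.** Let c be the share of malignant cases converted.

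- Days saved per converted case: 0.6 × (194.5 − 14) + 0.4 × (365 − 14) = 108.3 + 140.4 = 248.7.
- Mean per participant, 0.75 × c × 248.7: 130.6, 93.3 and 56.0 for c = 0.7, 0.5 and 0.3.
- Later diagnoses among those still at risk in the proposed pathway, 0.75(1−c) × 0.6 / (1 − 0.75c): 0.284, 0.360 and 0.406. The standard pathway has 0.75 × 0.6 = 0.45.
- Ratio of cumulative hazards, ln(1 − later share) / ln(0.55): 0.56, 0.75 and 0.87. This agrees with the simulated ratios after day 30.

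**Step 3. Origin at enrolment, as section 7.3 has it.** Index diagnoses have time at or below zero, and a risk set that opens at enrolment omits them. In set A what remains is essentially the after-day-30 ratio, 0.55 to 0.88, while 56 to 130 days are saved. In set B, removing the index diagnoses gives 0.98, 0.97 and 0.99 at 12 months for index yields of 20%, 40% and 60%. The ratio does not respond to the index yield. These runs remove the index records but do not give each participant a separate interval from biopsy to enrolment.

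**Step 4. Add gains at repeat biopsies.** With a further 30% gaining at the repeat biopsy, set B at 12 months gives 1.62, 2.07 and 3.00 from the index biopsy, and 1.34, 1.36 and 1.38 with index diagnoses removed. The second series still barely moves while the index yield triples. In set A at 50% conversion the ratio falls from 12.1 (90 days) to 2.2 (365 days), and the ratio after day 30 lies between 0.75 and 1.25 across scenarios.

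**The case against.** Four counter-arguments deserve weight.

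1. **Not all the benefit is at the index biopsy.** A reader might infer that everyone not converted there keeps the same date and that the later ratio can never exceed 1. The Protocol does not support this: repeat biopsies are tested too, and Step 4 shows later ratios above 1. This stands.
2. **Follow-up is fixed.** A reader might infer that the ratio mainly reflects the length of follow-up. It does not. The plan has 12 months, already completed, and at that horizon the ratio from the index biopsy rises with marker performance (1.4, 1.9 and 2.4 in set A). In set B at 40% yield it moves only from 1.76 to 1.67 between 6 and 12 months, about 5%. What remains is that it depends on follow-up and has no meaning as a constant relative rate.
3. **Stratifying by participant might rescue the model.** A reader might infer that such a model must diverge. That holds only with exact tie handling or with no tied pairs. With c conversions and m pairs diagnosed on the same date, Efron and Breslow both give (c + m)/m: for c = 13, m = 13 this is 26/13 = 2.0; for c = 22, m = 13 it is 35/13 = 2.69. The value is finite, but only because same-date pairs are treated as evidence for a ratio of 1. It does not express time saved.
4. **The analysis plan may add checks and other summaries.** Section 10 also promises tabulation and descriptive comparison, and it does not rank the secondary outcomes. That is fair, and it limits the weight of the point. But the Protocol names this model, and a proportional-hazards check would only confirm a failure already built into the design.

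An analyst could also keep index diagnoses by assigning them a small positive time. That restores the block of events against none in Step 1.

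**Conclusion.** The point holds as a limited one. For time to diagnosis, the named Cox model is unsuitable under either origin. From the index biopsy, hazards are non-proportional by construction. From enrolment, the main gain drops out of the fit and the ratio can be near or below 1. Moving the origin or handling the pairing does not by itself cure this.

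On size, with gains at the index biopsy alone the 12-month ratio is about 1.3 to 2.4 from that biopsy and about 0.55 to 1.0 with index diagnoses removed. Repeat-biopsy gains raise the latter to about 1.34 to 1.38 in set B. All these values, and the 56 to 130 days saved, rest on assumed malignancy rates, timings and yields, and are illustrative. With different diagnosis times inside the same 44 to 345 day span, the days saved were 115, 83 and 51. The structural conclusion needs only the eligibility rule, the location of the primary gain and the stated time origin.

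This should be changed. It concerns a secondary outcome and does not touch the primary comparison.

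**What to change.** In section 10, for time to diagnosis, replace the Cox hazard ratio as the main summary with the within-participant difference in days, standard minus proposed, and measure both times from the index biopsy. Amend section 7.3 so that the origin agrees.

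Report the median difference and the restricted mean difference over a fixed horizon, with a 95% interval from a bootstrap that resamples participants. Show the cumulative diagnosis curves of both pathways. The restricted mean is needed beside the median. If half of malignant cases convert and 75% are malignant, only 0.75 × 0.5 = 37.5% of participants gain at the index biopsy, and without repeat-biopsy gains the median difference is zero. State the horizon, and the handling of participants undiagnosed at it or who die first, before the data are examined.

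The cost is a wording change. Biopsy dates and the date of diagnosis are already on the extraction list, so no new data are needed. The study gives up a hazard ratio as its main summary and gains a result in days, which is what its time-to-diagnosis objective asks for.
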